#### **9.2.4 Visit 2 (Day 21 ± 3 days) and Visit 3 (Day 42 ± 4 days)**

Visits 2 and 3 will consist of an on-site visit. These visits should coincide with the normal timing of dressing changes, i.e. seven (7) days or fewer for ALNB.

Subjects who have already had their treatment discontinued/been withdrawn from treatment and no longer require a dressing change shall be followed up either by an on-site visit or by telephone. In such cases, the main purpose will be to collect CWIS outcome data and any data related to AE (if applicable).

- 1. Question subjects regarding any changes in health or concomitant treatment.
- 2. All subjects must complete the CWIS, including those withdrawn from treatment unless they have been withdrawn from the study.

Give the subject a printed copy of the CWIS and allow sufficient time to complete it. Assist with completion if asked. For any subject followed up by telephone, read the complete CWIS and record the subject's responses accurately. Ensure that the subject has completed the CWIS appropriately. A single valid response should be recorded for each item.

NOTE: subjects who cannot read/write may have the CWIS read aloud to them and the subject's responses recorded. Ensure this process is noted in the source documents.

3. Ask the subject to assess the comfort of wearing the dressing since the last visit (see Section 9.5.8).
4. Assess the movement of the dressing (see Section 9.5.9).
5. Remove the old dressing and inspect the ulcer. Complete an ulcer assessment (see Section 9.5.1).

*Notes: 1) A full ulcer assessment is not necessary if the subject has already been discharged or withdrawn from treatment.*

*2) Not applicable if this visit is completed via a phone call.*

6. Assess the level of pain experienced by the subject when the dressing is removed (see Section 9.5.6).
7. Assess the ease of dressing removal, leakage, and absorption under compression (see section 9.5.10)
8. Take a photograph of the ulcer, showing the ruler as supplied. Record any debridement and the method of debridement, and take a photograph of the ulcer immediately prior to and following debridement.

Photograph the used dressing on both sides, together with any secondary dressing.

Note: Photographs are not necessary if the subject was discharged or withdrawn from treatment at a previous visit.

9. Redress the ulcer, if clinically indicated, using an appropriate dressing according to group allocation:

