#### Healthcare resource use

The following Healthcare resource variables will be summarized by treatment groups and overall at twelve weeks:

- Number and type of dressings used (both primary and secondary dressings), including use of compression therapy
- Number of outpatient visits
- Amount of time in hospital (nights spent as an inpatient)
- Number and type of interventions/procedures including debridement of ulcer (curette, scissors, scalpel, forceps, other)
- Number and type of concomitant therapies/treatments

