5.3 Secondary Endpoints

Ulcer progression variables to be compared between groups at three, six, and twelve weeks including:

- Modified Bates-Jensen Wound Assessment Tool
 - Undermining
 - Necrotic tissue type
 - Necrotic tissue amount
 - Exudate type

CONFIDENTIAL AND PROPRIETARY

This document contains information that is confidential and proprietary to Smith & Nephew PLC and Smith & Nephew, Inc. and is intended for use only by Smith & Nephew and its manufacturer. It shall not be reproduced or copied in whole or in part, nor shall the contents be disclosed by any means without prior written permission from Smith & Nephew, nor shall anyone make any use of it that is contrary to the expressed or implied wishes of Smith & Nephew

Statistical Analysis Plan	
A Pilot Randomized Controlled Trial to Evaluate an Advanced Borderless Dressing (ALLEVYN™ LIFE Non-Bordered) in the Treatment of Chronic Ulcers	Number: CT1603ALF
	ST: 1005
	Version: 1.0, 27-Jul-2018
	Page: 11 of 27

- Exudate amount
- Skin color surrounding the wound
- Granulation tissue
- Epithelialization
- Condition of peri-wound
- Ulcer dimensions
- Ulcer healed status

Healthcare resource use variables (to be compared between groups over the entire twelve week study period) including:

- Dressings used (number and type for both primary and secondary dressings), including use of compression therapy
- Healthcare consultations (number and type)
- Time spent by health care providers (HCP) in treating/caring for reference ulcer
- Time in hospital (nights spent as an inpatient due to reference ulcer)
- Interventions/procedures related to the reference ulcer (number and type), including debridement of the ulcer (curette, scissors, scalpel, forceps, other)
- Concomitant therapies/treatments (number and type) used on the reference ulcer

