7.2 Analysis Populations

All subjects who provide informed consent are considered study participants. Study populations are defined as follows:

- **Safety population (SAF):** all subjects who receive study treatment. This population will be used for summaries of disposition of the subjects, protocol deviations/violations, and safety.
- **Full analysis set (FAS):** following the intention to treat principle all randomized subjects who receive study treatment and attend at least one post-baseline assessment will be included. This population will be used for the primary analysis of baseline characteristics, primary variables, secondary variables and exploratory variables.
- **Per protocol (PP) population:** includes all subjects in the FAS population who have no significant protocol deviations, meet the inclusion/exclusion criteria, and did not withdraw early (except for closure at any time). This population will be used for supportive evidence of the primary variable.

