If a subject has missing data for any values for length, width or depth of the wound at a particular visit, and has at least one post-baseline score, then the LOCF method will be used. The only exception to this is when missing values occur and the ulcer is healed, in which case 0cm (length/ width) or 0mm (depth) shall be imputed for all missing measurements in the statistical analysis.

Ulcer healed status

CONFIDENTIAL AND PROPRIETARY

This document contains information that is confidential and proprietary to Smith & Nephew PLC and Smith & Nephew, Inc. and is intended for use only by Smith & Nephew and its manufacturer. It shall not be reproduced or copied in whole or in part, nor shall the contents be disclosed by any means without prior written permission from Smith & Nephew, nor shall anyone make any use of it that is contrary to the expressed or implied wishes of Smith & Nephew

Statistical Analysis Plan	 Number: CT1603ALF ST: 1005 Version: 1.0, 27-Jul-2018 Page: 15 of 27
A Pilot Randomized Controlled Trial to Evaluate an Advanced Borderless Dressing (ALLEVYN™ LIFE Non-Bordered) in the Treatment of Chronic Ulcers	

If the ulcer healed status is missing at a particular assessment and the ulcer was marked as healed at the previous assessment then the ulcer should be classified as healed.

If the ulcer healed status is missing at a particular assessment and the ulcer was not marked as healed at the previous assessment then the ulcer should not be classified as healed. If the baseline ulcer healed status is missing then this should also be implemented as not healed.

In cases where the wound is recorded as healed in the investigators opinion the following imputations will be made if missing values are present: Signs of critical colonisation or infection = No. Level of Exudate = None.

Healthcare resource use

If any of the healthcare resource data is missing then no missing data implementation will be used.

Dressing Change

If any of the dressing change data from the exploratory endpoints is missing then no missing data implementation will be used.

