- Ulcer length/width/depth will be used to derive area and volume. These variables will then be used to derive the reduction in area, depth, and volume from baseline to three, six and twelve weeks. The reduction in each dimension at each assessment (3, 6 and 12 weeks) will be analysed as the dependent variable in separate ANCOVA models. As a minimum the models will contain a term for treatment. The following terms will be added to the model using a stepwise selection procedure with an F-value to attain a significance level of 0.1: centre, subject, wound type, BMI and the relevant baseline wound dimension (area/ depth/ volume). The estimate difference in the LSMean reductions from baseline in area, depth, and volume (separately) between treatments will be presented with the associated 95% confidence interval.
- Reference ulcer healed (100% re-epithelialized, no drainage, no need for a dressing) will be summarized at each assessment (at three, six, and twelve weeks) and analyzed using a repeated measures logistic regression model with whether the reference ulcer was healed or not at the assessment as the dependent variable. As a minimum the model will contain a term for treatment. The following terms will be added to the model using a stepwise selection procedure with an F-value to attain a significance level of 0.1: centre, wound type and BMI..

Healthcare resource use

CONFIDENTIAL AND PROPRIETARY

This document contains information that is confidential and proprietary to Smith & Nephew PLC and Smith & Nephew, Inc. and is intended for use only by Smith & Nephew and its manufacturer. It shall not be reproduced or copied in whole or in part, nor shall the contents be disclosed by any means without prior written permission from Smith & Nephew, nor shall anyone make any use of it that is contrary to the expressed or implied wishes of Smith & Nephew

Statistical Analysis Plan	
A Pilot Randomized Controlled Trial to Evaluate an Advanced Borderless Dressing (ALLEVYN™ LIFE Non-Bordered) in the Treatment of Chronic Ulcers	Number: CT1603ALF
	ST: 1005
	Version: 1.0, 27-Jul-2018
	Page: 24 of 27

The following Healthcare resource variables will be summarized by treatment groups and overall (i.e. all assessments together) using continuous or categorical data summaries (as appropriate):

- Number and type of dressings used (both primary and secondary dressings), including use of compression therapy
- Number of outpatient visits

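### Twelve-week resource-use summaries make no allowance for time observed, so unequal study withdrawal can create a false difference between arms

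*SAP*

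**What the plan says.** SAP 5.3 lists dressings, consultations, provider time, nights in hospital, procedures and concomitant treatments as secondary endpoints, "to be compared between groups over the entire twelve week study period". The analysis in SAP 7.11 is that these variables are "summarized by treatment groups and overall (i.e. all assessments together) using continuous or categorical data summaries". The matching text in Protocol 10.2.2.2 reads: "The following Healthcare resource variables will be summarized by treatment groups and overall at twelve weeks". Neither gives a rate, an offset or a censoring time.

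The missing-data rule in SAP 7.3 is one sentence: "If any of the healthcare resource data is missing then no missing data implementation will be used". SAP 7.2 assigns secondary variables to the full analysis set, in which "all randomized subjects who receive study treatment and attend at least one post-baseline assessment will be included". Completing twelve weeks is not a condition.

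The plan does derive or report time variables. SAP 7.4 has treatment duration and days from baseline to each visit, and SAP 7.6 summarises study duration by arm. None is linked to resource use, and SAP 7.15 records no change on the point.

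**The concern.** A count cannot grow after a subject has left the study. Those weeks do not appear in the data as blank fields; in a per-subject count they look the same as weeks with no use. Protocol 7.6 allows complete withdrawal for several reasons, including withdrawn consent, concurrent illness, an adverse device effect, non-compliance and loss to follow-up. The trial is open-label, with one arm on a single product and the other on dressings of the investigator's choice, so unequal loss is plausible. With 15 standard care subjects, one departure is 6.7% of that arm.

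The stated aim in Protocol 5 and SAP 4 includes preliminary health-economic data for planning cost-effectiveness research. These summaries are the data meant for that use. A difference produced by follow-up time alone would be carried into that planning as if it were a difference in use.

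**Working it through.** **Plan's own figure.** The only figure that can be reproduced is the sample size in SAP 6.1: 25 ALNB subjects at 5:3 give 25 × 8/5 = 40 in total and 25 × 3/5 = 15 on standard care. This agrees with the plan. It states no withdrawal or resource-use figure.

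**Inputs.** n = 25 and 15 (Protocol synopsis). Follow-up is 12 weeks. True weekly rate r = 1 in both arms, for illustration, in line with the minimum of weekly site visits (SAP 3). The number leaving the study, k, and the week of leaving, t, are assumptions, so a range is shown.

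**Formula.** Expected mean count per subject = r × [(n − k) × 12 + k × t] / n.

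Example, 4/15 standard care and 3/25 ALNB leaving at week 4:
- Standard care: (11 × 12 + 4 × 4)/15 = 148/15 = 9.87
- ALNB: (22 × 12 + 3 × 4)/25 = 276/25 = 11.04
- Ratio 11.04/9.87 = 1.12, though the true ratio is 1.00

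| Leave ALNB | Leave SC | Week | Mean ALNB | Mean SC | Ratio ALNB/SC |
|---|---|---|---|---|---|
| 3/25 | 2/15 | 4 | 11.04 | 10.93 | 1.01 |
| 3/25 | 4/15 | 4 | 11.04 | 9.87 | 1.12 |
| 0/25 | 3/15 | 1 | 12.00 | 9.80 | 1.22 |
| 0/25 | 3/15 | 3 | 12.00 | 10.20 | 1.18 |
| 0/25 | 3/15 | 6 | 12.00 | 10.80 | 1.11 |
| 5/25 | 0/15 | 1 | 9.80 | 12.00 | 0.82 |
| 5/25 | 1/15 | 6 | 10.80 | 11.60 | 0.93 |
| 5/25 | 3/15 | 3 | 10.20 | 10.20 | 1.00 |

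The ratio does not depend on r, which cancels. The direction follows the arm that loses more time. In the last row both arms lose 20% at the same week and the ratio is exact.

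The week 1 rows assume that a routine dressing-change visit counts as a post-baseline assessment. If only the scheduled visits count, nobody who leaves before about week 3 enters the full analysis set, and the largest ratio for 3/15 against 0/25 is 1.18.

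**Per subject-week observed.** In the example, standard care has 148 uses in 148 weeks and ALNB 276 in 276: 1.00 in both. This holds when the rate is constant and leaving is unrelated to use.

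**If use is front-loaded.** Assume 2 per week in weeks 1 to 4, then 1 per week, with the same withdrawals. A completer has 8 + 8 = 16 uses and a leaver 8.
- Totals: standard care (11 × 16 + 4 × 8)/15 = 208/15 = 13.87; ALNB (22 × 16 + 3 × 8)/25 = 376/25 = 15.04; ratio 1.08
- Rates: 208/148 = 1.41 and 376/276 = 1.36; ratio 0.97

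The rate reduces a false 8% difference to a false 3% in the opposite direction. It does not remove it.

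**The case against.** The strongest reply is that the SAP never says a per-subject sum will be formed. SAP 7.4 derives none, and the words about all assessments together explain what overall means. Subjects with incomplete follow-up might be left out altogether. That stands as a point about wording: the handling is unspecified. It does not remove the problem, because a complete-case summary replaces truncation with selection.

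Exposure is also limited. Under Protocol 9.2.6 subjects withdrawn only from treatment stay in the study to week 12. Protocol 9.2.7 captures site visits for the reference ulcer, and Protocol 9.3 seeks an End of Study Visit, where possible, even from those who discontinue the study. SAP 7.6 would show unequal follow-up by arm. All of this narrows the issue to full study withdrawal, but none of it ensures that use after study exit is recovered or puts a denominator into the resource tables.

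A reader might infer that counts also stop once follow-up goes by telephone, since Protocol 9.2.4 says "the main purpose will be to collect CWIS outcome data and any data related to AE". The documents do not support that as a general statement. The sentence concerns subjects off treatment whose ulcer needs no further dressing, so little ulcer-related use would be expected. They are still asked about changes in health and treatment, and Protocol 9.2.8.2 records treatments for the reference ulcer. Protocol 9.2.5 lacks the dressing qualifier at week 12, so a small gap may remain.

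Finally, the summaries carry no planned test or interval, in a pilot sized on feasibility. That is right, and it limits the consequence.

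**Conclusion.** The concern holds as a gap in a descriptive secondary analysis. As planned, the twelve-week comparison makes no allowance for time observed, and unequal study withdrawal would distort it. Across the assumed scenarios with unequal withdrawal the false difference runs from about 1% to about 22%, with recorded use understated in the arm that loses more time. It is zero when withdrawal matches in frequency and timing. These figures rest on assumed withdrawals, equal constant weekly rates, and leaving that is unrelated to use.

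Two stronger readings are not supported. One is that an arm would look cheaper: cost is in the objective (SAP 4.3), but SAP 7.11 has no costing step, so only recorded use is affected. The other is that the bias favours a particular arm or is bound to occur: the documents give no basis for predicting withdrawal. The primary and key secondary results are untouched.

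**What to change.** In SAP 7.11:

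- Define each subject's resource observation window as baseline to last study contact. Count subjects whose ulcers have healed, or who are withdrawn only from treatment, until their last study contact, normally week 12. Lower use after healing is a real effect and should keep its full time at risk.
- Report each count also as a descriptive rate per subject-week observed, by arm.
- Show raw totals for twelve-week completers beside the rate.
- State in SAP 7.3 that use after study exit is unobserved and is not to be read as zero use.

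No inferential count model is needed. With 25 and 15 subjects, and possibly sparse outcomes such as hospital nights, it could be unstable and would add little.

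The cost is SAP wording and one more column per table, using dates already collected. The rate assumes that use after leaving resembles use before and is roughly constant over time; front-loaded use leaves some residual bias. The completer totals are open to selection, which is why the two are shown together.

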7.4 Derived Data

Analysis Populations

- Indicator for inclusion in the safety population.
- Indicator for inclusion in the full analysis set population.
- Indicator for inclusion in the per protocol population.

Demographics, Baseline Data and Disposition Data

- Age = (Date of baseline visit – date of birth) /365.25

Note: Round down to the nearest whole number.

CONFIDENTIAL AND PROPRIETARY

This document contains information that is confidential and proprietary to Smith & Nephew PLC and Smith & Nephew, Inc. and is intended for use only by Smith & Nephew and its manufacturer. It shall not be reproduced or copied in whole or in part, nor shall the contents be disclosed by any means without prior written permission from Smith & Nephew, nor shall anyone make any use of it that is contrary to the expressed or implied wishes of Smith & Nephew

Statistical Analysis Plan	
A Pilot Randomized Controlled Trial to Evaluate an Advanced Borderless Dressing (ALLEVYN™ LIFE Non-Bordered) in the Treatment of Chronic Ulcers	Number: CT1603ALF ST: 1005 Version: 1.0, 27-Jul-2018 Page: 16 of 27

- Body Mass Index (BMI)[kg/m²] = weight [lbs] * 703.07/ (height [inches])²

Note: the 703.07 is to correct for using pounds and inches.

- Ulcer duration = Date of baseline visit – Date of ulcer onset
- Treatment duration [days] = Date of treatment discontinuation – date of baseline assessment.
- Duration between visits = Date of Study Visit_i – date of baseline assessment, where i = 2,3,4
- A flag for if the study visit occurs outside of the time range defined in the protocol i.e. Study Visit 2 should occur on Day 21 ± 3 days, Study Visit 3 should occur on Day 42 ± 4 days, End of Study Visit should occur on Day 84 ± 4 days.

Cardiff Wound Impact Schedule

- CWIS PSDL Score =
$$\frac{\text{Sum of PSDL item scores} - 24}{96} * 100$$
- CWIS SL Score =
$$\frac{\text{Sum of SL item scores} - 14}{56} * 100$$
- CWIS WB Score =
$$\frac{\text{Sum of WB item scores} - 7}{28} * 100$$
- The CWIS-GQ score is the number circled for “How good is your quality of life”
- The CWIS-PQ score is the number circled for “How satisfied are you with your overall quality of life”
- The below formula for individual domain increases from baseline applies to all the above mentioned CWIS domains:

CWIS domain Score increase = Score at visit_i – Score at baseline visit, i = 2,3,4

CONFIDENTIAL AND PROPRIETARY

This document contains information that is confidential and proprietary to Smith & Nephew PLC and Smith & Nephew, Inc. and is intended for use only by Smith & Nephew and its manufacturer. It shall not be reproduced or copied in whole or in part, nor shall the contents be disclosed by any means without prior written permission from Smith & Nephew, nor shall anyone make any use of it that is contrary to the expressed or implied wishes of Smith & Nephew

Statistical Analysis Plan	
A Pilot Randomized Controlled Trial to Evaluate an Advanced Borderless Dressing (ALLEVYN™ LIFE Non-Bordered) in the Treatment of Chronic Ulcers	Number: CT1603ALF ST: 1005 Version: 1.0, 27-Jul-2018 Page: 17 of 27

Ulcer Progression

- Scoring system for all items of the Modified Bates-Jensen Wound Assessment Tool can be found in the Study Protocol.
- The total Modified Bates-Jensen Score will be calculated by summing the scores from each item.
- If the maximum depth of the wound is marked as superficial then set depth to 0mm.
- Ulcer area [cm²] = length [cm] x width [cm] x (π/4)
- Ulcer volume [cm³] = area [cm²] x (depth [mm] / 10)
- For each post-baseline study visit, the percentage reduction ulcer area from baseline assessment will be derived as:

$$\% \text{ reduction in area at Study Visit}_i = \left(\left(\frac{\text{Area}_{SV1} - \text{Area}_{SVi}}{\text{Area}_{SV1}} \right) \times 100 \right), \quad i = 2,3,4$$

The same method will be used to derive percentage change in volume and depth.

- For each study visit, the absolute reduction in ulcer area will be derived as:

$$\text{Absolute reduction in ulcer area at Study Visit}_i = \text{Area}_{SV1} - \text{Area}_{SVi}, \quad i = 2,3,4$$

The same method will be used to derive percentage change in volume and depth.

Dressing Details

- Dressing wear time (measured in days) will be derived as:

$$\text{Wear time} = \text{Date of dressing removal} - \text{Date of dressing application}$$

- The average wear time over all applications per subject will be derived as follows:

$$\text{Average Wear Time [per subject]} = \frac{\text{Sum of wear time values}}{\text{Count of wear time values}}$$

CONFIDENTIAL AND PROPRIETARY

This document contains information that is confidential and proprietary to Smith & Nephew PLC and Smith & Nephew, Inc. and is intended for use only by Smith & Nephew and its manufacturer. It shall not be reproduced or copied in whole or in part, nor shall the contents be disclosed by any means without prior written permission from Smith & Nephew, nor shall anyone make any use of it that is contrary to the expressed or implied wishes of Smith & Nephew

Statistical Analysis Plan	
A Pilot Randomized Controlled Trial to Evaluate an Advanced Borderless Dressing (ALLEVYN™ LIFE Non-Bordered) in the Treatment of Chronic Ulcers	Number: CT1603ALF ST: 1005 Version: 1.0, 27-Jul-2018 Page: 18 of 27

Adverse Events

- Individual flags for whether each adverse event was a serious adverse event, severe adverse event, investigational device related adverse event, a serious investigational device related adverse event, an unexpected adverse event and a serious unexpected adverse event.
- The duration of adverse events defined as:

Duration of resolved AE = End date – start date

Duration of unresolved AE = Date of study completion – start date

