### 9.2.6 Treatment Discontinuation

A subject may be withdrawn from treatment early and discharged from care (see Sections 7.6 and 9.3) prior to follow-up at Visit 2, Visit 3, or the End of Study Visit. However, these subjects will still be retained as active study participants, even though their study treatment has ended. When this occurs, the subject will continue as an active participant for the remainder of the twelve (12) week study period, completing all remaining study visits (either by attending site appointments or by telephone if necessary), to gather complete CWIS data.

1. Question subjects regarding any changes in health or concomitant treatment.
2. Give subject given a copy of the CWIS and allow sufficient time for them to complete it. Assist with completion if asked. For any subject followed up by telephone (see above), read the complete CWIS and record the subject's responses accurately. Ensure that the subject has completed the CWIS appropriately. A single valid response should

be recorded for each item of the CWIS.

NOTE: subjects who cannot read/write may have the CWIS read aloud to them and the subject's responses recorded. Ensure this process is noted in the source documents.

3. Ask the subject to assess the comfort of wearing the dressing since the last visit (see Section 9.5.8).
4. Assess the movement of the dressing. (see Section 9.5.9).
5. Remove the old dressing and inspect the ulcer. Complete an ulcer assessment (see Section 9.5.1).

*Notes: 1) A full ulcer assessment is not necessary if the subject has already been discharged or withdrawn from treatment.*

*2) Not applicable if this visit is completed via a phone call.*

6. Assess the level of pain experienced by the subject when the dressing is removed. (see Section 9.5.6).
7. Assess the ease of dressing removal, leakage, and absorption under compression (see section 9.5.10).
8. Take a photograph of the ulcer, showing the ruler as supplied. Record any debridement and method of debridement, and take a photograph of the ulcer immediately prior to and after debridement.

Photograph the used dressing on both sides, together with any secondary dressing.

9. If any AE or DevD are observed or reported, they must be recorded as instructed in Section 12 (Adverse Events and Device Deficiencies).

Photograph the dressing only if reporting a device deficiency.

10. Redress the ulcer, if clinically indicated, using an appropriate dressing.  

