Do not apply any dressing supplied by S&N for use within the study, as the study treatment is being discontinued.

11. Record details of any new dressings applied and complete all remaining items in the eCRF.

12. Instruct the subject on the need to continue as a participant in the study, providing important information about their health and quality of life, until the End of Study Visit ( $84 \pm 4$  days from Visit 1).

13. If ongoing treatment is clinically indicated, continue to provide the subject with SC for the remainder of the study.

14. Record the total time that the subject spent at the visit (start to finish of ulcer care procedures).

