### **9.2.7 Unscheduled Visits**

Any visits to the research site due to the reference ulcer will be captured as a Routine Dressing Change Visit (Section 9.2.3). Visits to the research site for other reasons may be captured as an Unscheduled Visit at the discretion of the Investigator with all information recorded in the source documents and on the Unscheduled Visit eCRF.

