7.12 Analysis of Exploratory Endpoints

- The average dressing wear time (days) per subject will be calculated and this will be summarized as a continuous variable by treatment group and overall. An estimate of the difference in wear time between treatment groups will be reported with the corresponding 95% confidence interval at twelve weeks only.
- Dressing leakage will be summarized by treatment group and overall
- Ease of dressing application/removal will be summarized by treatment group and overall
- Dressing use (whether dressing was cut and adherence following repositioning) will be summarized by treatment group and overall
- Durafiber/ Intrasite use will be summarised
- Odor control of dressing will be summarized by treatment group and overall
- Absorption of exudate under compression will be summarized by treatment group and overall.
- Reason for dressing change will be summarized by treatment group and overall

CONFIDENTIAL AND PROPRIETARY

This document contains information that is confidential and proprietary to Smith & Nephew PLC and Smith & Nephew, Inc. and is intended for use only by Smith & Nephew and its manufacturer. It shall not be reproduced or copied in whole or in part, nor shall the contents be disclosed by any means without prior written permission from Smith & Nephew, nor shall anyone make any use of it that is contrary to the expressed or implied wishes of Smith & Nephew

Statistical Analysis Plan	 Number: CT1603ALF ST: 1005 Version: 1.0, 27-Jul-2018 Page: 25 of 27
A Pilot Randomized Controlled Trial to Evaluate an Advanced Borderless Dressing (ALLEVYN™ LIFE Non-Bordered) in the Treatment of Chronic Ulcers	

- Pain on dressing removal will be summarized by treatment group and overall and an estimate of the difference between treatment groups will be reported with the corresponding 95% confidence interval.
- Comfort during wear will be summarized by treatment group and overall

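### Wear time is averaged over every dressing a subject wore, so dressings used after allocated treatment stops count towards the randomised arm

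*SAP*

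**What the plan says.** The exploratory objective (SAP 4.4, Protocol 5.4) is to compare ALNB with SC on dressing performance, including wear time, and on usability.

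SAP 7.4 defines wear time as removal date minus application date, and then: "The average wear time over all applications per subject will be derived as follows". The formula is the sum of a subject's wear times divided by their count. SAP 7.12 summarises this average by treatment group and reports the between-group difference with a 95% confidence interval at twelve weeks. The other dressing variables are treated in the same unrestricted way, for example: "Dressing leakage will be summarized by treatment group and overall". SAP 7.2 assigns exploratory variables to the FAS, which follows intention to treat.

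On stopping treatment, Protocol 9.2.6 says of the subjects concerned: "these subjects will still be retained as active study participants, even though their study treatment has ended". At that visit: "Do not apply any dressing supplied by S&N for use within the study, as the study treatment is being discontinued". The new dressing is documented: "Record details of any new dressings applied and complete all remaining items in the eCRF". Afterwards: "If ongoing treatment is clinically indicated, continue to provide the subject with SC for the remainder of the study". Protocol 9.2.7 adds: "Any visits to the research site due to the reference ulcer will be captured as a Routine Dressing Change Visit". It makes no exception for subjects who have stopped treatment.

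**The concern.** Wear time is a property of a dressing. Once an ALNB subject has stopped ALNB, the dressings that follow are SC products, and Protocol 6.1.2 excludes any ALLEVYN variant from SC. Their wear times say nothing about how ALNB performs, yet the stated rule credits them to the ALNB arm. Because the formula divides by the number of dressings, whichever product is changed more often has more weight in that subject's average.

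The SC arm is not immune. Protocol 7.6 lets the investigator withdraw a subject of either arm from study treatment for a clinically warranted change. An SC subject withdrawn for that reason may receive a product that Protocol 6.1.2 keeps out of SC, and its wear time would be counted as SC.

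At stake is the wear-time difference and its confidence interval, which the trial would report as a comparison of dressings and could carry into the planning of later studies. No other planned analysis supplies an on-treatment version: SAP 7.2 uses the per-protocol set only to support the primary variable, and SAP 7.15 does not mention the matter.

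**Working it through.** The plan states no wear time, expected difference or discontinuation rate, so there is no figure of its own to reproduce. The check has two parts.

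**Text.** Each link from stopping treatment to the reported average is present:

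1. Treatment may end early for reasons other than closure (Protocol 7.6).
2. No study-supplied sponsor dressing is applied from then on, and SC is given if the ulcer still needs treating (Protocol 9.2.6, steps 10 and 13).
3. The subject stays to week 12 and the new dressings are recorded (Protocol 9.2.6); visits for the ulcer use the routine dressing-change record (Protocol 9.2.7).
4. Analysis is by randomised group in the FAS (SAP 7.2).
5. Wear time is averaged over all applications, with no exclusion (SAP 7.4), and compared by group (SAP 7.12).

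**Size, by illustration.** From the documents: an 84-day period and the SAP 7.4 formula. Assumed: ALNB wear wA, SC wear wS, stopping day t, and the share f of the ALNB arm that stops and is then dressed with SC to day 84. Stopping is taken to be unrelated to a subject's own wear time.

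- Average for a subject who stops: 84 / (t/wA + (84 - t)/wS)
- ALNB arm mean: (1 - f) × wA + f × that average
- Reported difference: arm mean - wS; with the limit in place it is wA - wS

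Take wA = 5, wS = 3 and t = 42. The subject has 42/5 = 8.4 ALNB and 42/3 = 14 SC dressings, and an average of 84/22.4 = 3.75 days. Weighting by days would give (42 × 5 + 42 × 3)/84 = 4.00; the count weighting pulls it further towards SC.

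- f = 10%: arm mean 0.9 × 5 + 0.1 × 3.75 = 4.875; difference 1.875 instead of 2.00, a loss of 6.25%.
- f = 20%: arm mean 0.8 × 5 + 0.2 × 3.75 = 4.75; difference 1.75, a loss of 12.5%.

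Shrinkage of the 2-day difference for other values, same wear times:

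| Stopping day | 10% stop | 20% stop | 40% stop |
|---|---|---|---|
| 21 | 8.3% | 16.7% | 33.3% |
| 42 | 6.25% | 12.5% | 25.0% |
| 63 | 3.6% | 7.1% | 14.3% |

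If SC is the longer-worn dressing (wA = 3, wS = 5), the difference also moves towards zero, by about 2% to 26% over the same grid. If both are worn for 4 days, it does not move.

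**The case against.** **Capture after discontinuation is less certain for the other dressing variables.** The routine dressing-change procedure (Protocol 9.2.3, step 8) redresses according to randomisation, so it reads as written for subjects on treatment. Telephone follow-up is allowed after stopping. Protocol 9.2.5 asks only for CWIS and adverse-event information at week 12 from subjects withdrawn from treatment, and Protocol 9.2.4 is similar for those who no longer need a dressing change. The treatment-discontinuation column of SAP Table 3.1 has no tick for dressing change or pain scale. This stands. A reader might infer that every dressing variable is affected; the documents establish that firmly only for wear time.

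**This is an estimand choice.** The FAS is specified for exploratory variables, and analysis by randomised group is legitimate. That holds for CWIS and resource use. It does not fit a question about how a dressing performs. Nor does an on-treatment limit hide ALNB failures, since a subject who stops because ALNB performed badly still contributes every ALNB application.

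**The shift is small against the noise.** Assuming a between-subject SD of 1.5 days, the 95% interval for 25 versus 15 subjects has a half-width of about 2.02 × 1.5 × √(1/25 + 1/15) = 1.0 day, against a shift of 0.125 to 0.25 day above. This stands as a comment on importance, but the shift is systematic and avoidable.

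**The tables, figures and listings shells may already set the limit.** They were not available for this review. The SAP text itself says all applications and excludes none.

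**Conclusion.** The wear-time rule, read as written, mixes dressings used after allocated treatment stops into the randomised arm's average, contrary to the stated aim of comparing dressing performance. The direct case is SC dressings in the ALNB average; the reverse case, non-allocated products in the SC average, is possible. The size cannot be computed from the documents. Under the assumptions of 5 versus 3 days and 10-20% stopping at day 42, the difference shrinks by about 6-12.5%. It is unchanged if wear times are equal, and smaller if those who stop have closed ulcers, leave the study or are followed by telephone.

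Three stronger readings are not supported:

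- **That contamination runs one way only.** SC subjects can also leave their allocated treatment (Protocol 7.6 with 6.1.2).
- **That the evidence for the product claims is undermined.** Protocol 8.2 ties the key claims to the CWIS-PSDL scale, which this issue does not touch, and its list does not name wear time. Protocol 5.6 says only that the pilot may supply preliminary support.
- **That the error is typically 11-18% or more.** That range needs 6 versus 2 days of wear and 3 to 5 of 25 subjects stopping at day 18: 84/(3 + 33) = 2.33 days each, giving arm means of 5.56 to 5.27 instead of 6.0. It is an assumed, unfavourable case.

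The consequence is limited to exploratory endpoints in an unpowered pilot. It is still worth correcting before analysis, because the trial is open-label and the choice should not be left to programming.

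**What to change.** In SAP 7.4 and 7.12, for both arms, derive wear time only from applications of the allocated treatment made before the date of treatment discontinuation. A dressing applied before that date and removed at the discontinuation visit still counts. Apply the same limit to the other dressing-performance and usability summaries wherever records exist after discontinuation. List later dressings separately by subject and product. Leave CWIS outcomes and resource use by randomised group as they are.

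The cost is about one sentence in each section and no new data: SAP 7.4 already uses the discontinuation date for treatment duration, and the protocol already records dressing brand (9.2.2, 9.2.3, 9.2.4). The downside is fewer dressing records from subjects who stop early. The result will describe dressing performance on treatment rather than an intention-to-treat effect, and should be labelled as such.
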